11.1.2.3.1 Statistical Methods

Descriptive statistics including 95% two-sided confidence intervals will be used to summarize the percentage of subjects with at least 50% reduction from baseline in 24-hour pad weight at device activation, and 6 months post device activation.

11.1.2.4. Secondary Endpoint 4 – 75% Reduction in pad weight

The endpoint is the proportion of subjects with at least 75% reduction from baseline in urinary incontinence as measured by 24-hour pad weight test at device activation, 6 months and 12 months post device activation.

11.1.2.4.1 Statistical Methods

Descriptive statistics including 95% two-sided confidence intervals will be used to summarize the percentage of subjects with at least 75% reduction from baseline in 24-hour pad weight at device activation, 6 months and 12 months post device activation.

11.1.2.5. Secondary Endpoint 5 – number of pads per day

The endpoint is change in number of pads per day at 3 months, 6 months and 12 months post device activation compared to baseline.

11.1.2.5.1 Statistical Methods

Descriptive statistics (N, mean, standard deviation, minimum, Q1, median, Q3 and maximum) will be used to summarize the number of pads per day at Baseline, 3 months, 6 months and 12 months post device activation along with change and percent change from baseline when applicable.

11.2. General Statistical Methods

The Intent-to-Treat (ITT) subject population includes all subjects who provide written informed consent to be enrolled into the study, and have a surgery initiated (defined as the first incision).

The As Treated (AT) Population includes all subjects for whom implantation of the device is successful.

The Per Protocol (PP) population includes all subjects in the AT Population who meet all eligibility criteria and have no major protocol deviations.

The endpoint analyses will be performed for the ITT population. The AT and PP populations will be evaluated as sensitivity analyses for the primary endpoint, and the safety outcomes will also be assessed using AT population.

11.2.1. Control of Systematic Error/Bias

All subjects will be treated according to the directions in the Operating Manual and Instructions for Use.

The primary endpoint analysis based on the exact binomial test is specified to be conservative in order to avoid bias toward demonstrating the primary hypothesis (i.e., achieving the performance goal) of the study. Furthermore, the potential of bias from missing data for the primary endpoint will be assessed through tipping point analysis.

11.2.2. Number of Subjects per Investigative Site

The study will be conducted at up to 30 sites. Sites will be encouraged to enroll a minimum of 5 subjects; a maximum of 25 subjects may be enrolled at a site, unless the site has received prior approval from the sponsor to enroll additional subjects.

11.3. Data Analyses

The analyses will include only the available cases unless specified otherwise. Presentation of summary statistics for continuous variables will include N, mean, median, standard deviation, minimum, and maximum values. For categorical variables, the number and percentage under each category will be presented.

11.3.1. Other Endpoints/Measurements

11.3.1.1. Additional Endpoint 1 – stress urinary incontinence episodes per day

The endpoint is change in number of stress urinary incontinence episodes per day at 6 months and 12 months post device activation compared to baseline. The stress urinary incontinence episodes are collected in the three day electronic diary.

11.3.1.1.1 Statistical Methods

For those patients without the continuous leakage at baseline, descriptive statistics (N, mean, standard deviation, minimum, Q1, median, Q3 and maximum) will be used to summarize the stress urinary incontinence episodes per day at baseline, 6 months and 12 months post device activation along with change and percent change from baseline when applicable.

For those patients with the continuous leakage at baseline, descriptive statistics (N, mean, standard deviation, minimum, Q1, median, Q3 and maximum) will be used to summarize the stress urinary incontinence episodes per day at 6 months and 12 months post device activation. If a subject experiences continuous leakage at a follow up visit, the number of stress urinary incontinence episodes will not be imputed.

Number and percentage of patients with continuous leakage will be reported separately at baseline, 6 months and 12 months post device activation.

Similar analyses will be performed for the other parameters collected in the three day electronic diary (urgency urinary incontinence episodes, fluid intake, and frequency of urination) when applicable.

11.3.1.2. Additional Endpoint 2 - IQoL

To evaluate the change in quality of life as measured by Incontinence Quality of Life (IQoL) at 3 months, 6 months and 12 months post device activation compared to baseline.

The endpoints are the IQoL total score and each of the three subscales of the IQoL, a 22 items tool quantifying the quality of life. The three subscales are the Avoidance & Limiting Behaviors (ALB), Psychosocial Impact (PS) and the Social Embarrassment (SE).

11.3.1.2.1 Statistical Methods

Descriptive statistics including 95% confidence intervals will be used to summarize the IQoL total scores and the three subscale scores at baseline, 3 months, 6 months and 12 months post device activation along with change from baseline.

11.3.1.3. Additional Endpoint 3 – IIQ-7

To evaluate the life impact of UI as measured by Incontinence Impact Questionnaire (IIQ-7) at 3 months, 6 months and 12 months post device activation compared to baseline.

The endpoint is the IIQ-7 score.

11.3.1.3.1 Statistical Methods

Descriptive statistics including 95% confidence intervals will be used to summarize the IIQ-7 score at baseline, 3 months, 6 months and 12 months post device activation along with change from baseline.

11.3.1.4. Additional Endpoint 4 – EQ-5D

To quantify the health states as measured by Health Status (EQ-5D) at 12 months post device activation compared to baseline.

The endpoints are EQ-5D descriptive system and EQ VAS, and it may be converted into a single index value.

11.3.1.4.1 Statistical Methods

For a categorical variable, the frequency or the proportion of a category will be calculated at baseline and 12 months post device implantation. For a continuous variable, descriptive statistics including 95% confidence intervals will be used to summarize the value at baseline, and 12 months post device activation.

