Artificial Urinary Sphincter Clinical Outcomes			
	AUSCO		
Planned Number of Subjects	Approximately 175 subjects will be enrolled in total to treat a minimum of 120 procedure subjects.		
Planned Number of Sites / Countries	Up to 30 sites will be activated in regions where the AMS 800 is commercially available, including but not limited to the United States, Europe, and Australia.		
Primary Endpoint	Treatment success defined as $\geq 50\%$ reduction in 24-hour pad weight test from baseline at 12 months post device activation.		
Secondary Endpoints	Incidence of safety parameters at 3 months, 6 months, and 12 months. Safety parameters include device and/or procedure related adverse events, revision rates, and serious adverse events		
	≥ 50% reduction in urinary incontinence as measured by 24-hour pad weight test at device activation and 6 months post device activation compared to baseline		
	≥ 75% reduction in urinary incontinence as measured by 24-hour pad weight test at device activation, 6 months, and 12 months post device activation compared to baseline		
	Reduction in # of pads per day at 3 months, 6 months and 12 months post-device activation compared to baseline		
Additional	Comparison of Pressure Regulating Balloons by subgroup analysis		
Endpoints	Change in numbers of stress urinary incontinence episodes, fluid intake, urgency urinary incontinence episodes, and frequency of urination based on 3-day electronic diary at 6 months and 12 months post device activation compared to baseline		
	Change in quality of life at 3 months, 6 months, and 12 months post device activation compared to baseline, as measured by the following questionnaires:		
	• IQoL		
	• IIQ-7		
	• EQ5D (12 Month)		
	• Subject Ease of Use (6 and 12 Month)		

Artificial Urinary Sphincter Clinical Outcomes				
AUSCO				
Method of Assigning Patients to Treatment	Patients are considered enrolled once they sign the informed consent form. Subjects will then undergo baseline data collection to confirm eligibility. All eligible subjects are treated with the AMS 800.			
Follow-up Schedule	Follow-up visits will occur at 3, 6, and 12 months after device activation. The study will be considered complete after all subjects have completed the 12-month follow-up visit. All follow-up visits may be conducted remotely or in clinic.			

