activation, 6 months, and 12 months post device activation compared to baseline Reduction in # of pads per day	more stringent measurement than primary endpoint
1 1	01.1
at 3 months, 6 months and 12 months post-device activation compared to baseline	Objective measurement of number of incontinence episodes per day. Common endpoint to assess urinary incontinence ^{9,10}
Comparison of Pressure Regulating Balloons by subgroup analysis Change in numbers of stress urinary incontinence episodes, fluid intake, urgency urinary incontinence episodes, and frequency of urination based on 3-day electronic diary at 6 months and 12 months post device activation compared to baseline	Compare different pressure regulated balloons Gather patient reported outcomes on device ^{9, 10}
Change in quality of life at 3 months, 6 months, and 12 months compared to baseline, as measured by the following questionnaires – IQoL, IIQ-7, EQ5D Subject Ease of Use questionnaire	Gain information on patient satisfaction and improvement in quality of life using validated questionnaires ¹⁰ Gain information specific to the patient's use of the
	at 3 months, 6 months and 12 months post-device activation compared to baseline Comparison of Pressure Regulating Balloons by subgroup analysis Change in numbers of stress urinary incontinence episodes, fluid intake, urgency urinary incontinence episodes, and frequency of urination based on 3-day electronic diary at 6 months and 12 months post device activation compared to baseline Change in quality of life at 3 months, 6 months, and 12 months compared to baseline, as measured by the following questionnaires – IQoL, IIQ-7, EQ5D Subject Ease of Use

7. Study Design

The study is a single arm, prospective, multi-center study with 12-month follow-up following device activation.

Page 21 of 62

The primary endpoint will be evaluated once all Intent-To-Treat (ITT) subjects have completed the 12-month study visit. All subjects will be followed to month 12, until study completion, or until discontinuation prior to month 12. All study procedures will be standardized for uniformity.

Physician specialty and site procedure location (such as private-practice, hospital, academic medical center, etc.) will be recorded in the site selection questionnaire.

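### EQ-5D is framed as a comparison with baseline, but its method summarises the two time points separately and specifies no within-man change

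*Combined protocol and SAP*

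**What the plan says.** **How the endpoint is framed.** The Protocol Synopsis places EQ-5D, marked for 12 months, under this heading: "Change in quality of life at 3 months, 6 months, and 12 months post device activation compared to baseline, as measured by the following questionnaires". Table 6.1-1 in Section 6 also lists it under change in quality of life, "as measured by the following questionnaires – IQoL, IIQ-7, EQ5D". Section 11.3.1.4 gives the aim as: "To quantify the health states as measured by Health Status (EQ-5D) at 12 months post device activation compared to baseline". The same section names the descriptive system and EQ VAS as the endpoints and makes conversion to a single index optional.

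**How it is analysed.** In Section 11.3.1.4.1, for categorical variables, "the frequency or the proportion of a category will be calculated at baseline and 12 months post device implantation". For continuous variables, "descriptive statistics including 95% confidence intervals will be used to summarize the value at baseline, and 12 months post device activation". The section mentions no change score, no interval for a change and no cross-tabulation of baseline against 12 months.

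**How the parallel endpoints are analysed.** The IIQ-7 method (11.3.1.3.1) summarises the score at baseline, "3 months, 6 months and 12 months post device activation along with change from baseline". The IQoL method (11.3.1.2.1) has the same clause. Pads per day (11.1.2.5.1) and the diary counts (11.3.1.1.1) add change and percent change where applicable.

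**General rules.** Section 11.3 states: "The analyses will include only the available cases unless specified otherwise". Section 11.2 applies the endpoint analyses to the ITT population. Neither section supplies a change score for EQ-5D or limits its baseline summary to men who also have a 12-month form.

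**The concern.** An analyst who follows 11.3.1.4.1 to the letter produces a baseline column and a 12-month column with different denominators. A reader will subtract one mean from the other, because the endpoint is presented as a comparison with baseline. That subtraction is not the average change in any fixed set of men. If the men without a 12-month form started lower, the 12-month mean will exceed the baseline mean even if nobody improved. If they started higher, a real improvement will be understated.

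The precision of the change is also lost. The interval for a within-man change depends on the correlation between a man's two scores, and this cannot be recovered from two separate intervals.

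EQ-5D is the only generic health measure in the study. Section 12 names it as the source of utility scores for an economic analysis that may follow. Leaving the change unspecified also leaves the choice between paired and unpaired presentation open until the data have been seen.

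**Working it through.** **1. The plan's own figures.** There is no sample size for EQ-5D. Section 11.1.1.2 gives 96 evaluable men and 120 procedures for the primary endpoint. With an exact one-sided binomial test, 65% under the null and 80% assumed, the rule at n = 96 is at least 72 successes. This gives type I error 0.0236 and power 0.909. Allowing for attrition, 96 / (1 − 0.20) = 120. Both figures reproduce. They are used here only for the expected loss: 120 − 96 = 24 men, and 24 / 120 = 0.20.

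**2. What the two columns contain.** EQ-5D is scheduled at baseline and 12 months only (Table 10.1-1, Sections 10.5 and 10.9). Under available cases, up to 120 men enter the baseline column and about 96 enter the 12-month column. The 96 are a subset of the 120.

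**3. Composition effect.** Let C be the baseline mean of the 96, D the baseline mean of the 24, and Y the 12-month mean of the 96.

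- Baseline column mean = 0.80 × C + 0.20 × D = C − 0.20 × (C − D).
- Difference of column means = Y − [C − 0.20 × (C − D)] = (Y − C) + 0.20 × (C − D).

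The first term is the real mean change in the men seen twice. The second is the artefact. The documents do not give C − D, so a range is assumed:

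| Assumed gap C − D (EQ VAS points) | Artefact at 20% attrition |
|---|---|
| 0 | 0 |
| 10 | 0.20 × 10 = 2.0 |
| 20 | 0.20 × 20 = 4.0 |

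In standard-deviation units, for assumed gaps of 0.25 to 0.8 SD:

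| Attrition | Artefact (SD) |
|---|---|
| 10% | 0.025 to 0.08 |
| 20% | 0.05 to 0.16 |
| 30% | 0.075 to 0.24 |

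A change computed in men with both assessments has no such term.

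**4. Precision.** Assume equal SDs at both times, and work in SD units.

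- SE of the paired change, n = 96, assumed correlation 0.5: √[2 × (1 − 0.5) / 96] = 0.1021.
- SE if a reader treats the two columns as independent: √(1/96 + 1/120) = 0.1369.
- Ratio: 0.1021 / 0.1369 = 0.745 to three decimals.

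As 95% half-widths, the paired interval is 0.24 SD at correlation 0.3, 0.20 SD at 0.5 and 0.15 SD at 0.7. The independent-columns half-width is 0.27 SD. The plan does not propose the independent-columns calculation; it is simply all that the two reported intervals allow.

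**The case against.** **The endpoint is minor and descriptive.** EQ-5D is an additional endpoint with no hypothesis test. Both forms are collected, so the change stays computable, and the economic analysis is only a possibility. This stands and sets the severity. It does not explain the omission, because IQoL and IIQ-7 are equally descriptive and do specify change.

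**The comparison is made.** Section 7.2 says that men act as their own controls, and both values are reported. A reader might infer that the stated endpoint is not analysed at all. That goes too far: 11.3.1.4 names the descriptive system and EQ VAS at 12 months against baseline, and both are tabulated. What is missing is the within-man change and its interval.

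**The columns share most of their men.** A reader might infer that two different groups are being compared. They are nested, with 96 of 120 (80%) in common at the planned attrition. The artefact exists only if dropouts differ at baseline; if they do not, the only loss is the paired summary.

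**The sizes are assumed.** The VAS gaps and the correlation have no source in the documents. The 20% is the allowance for the primary pad-weight endpoint, not an EQ-5D return rate. This stands, and is why a zero-gap case and a range are shown.

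**Pairing does not cure dropout.** This also stands. If the missing men had similar baselines but poor outcomes, a change computed in completers has the same selection bias as the 12-month column.

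**Two timing slips.** Table 6.1-1 places EQ-5D under 3, 6 and 12 months, and the categorical sentence in 11.3.1.4.1 counts from implantation where the continuous one counts from activation. A reader might infer extra assessments or a second 12-month time point. The documents support neither. The synopsis, Table 10.1-1 and Section 10.9 place the only follow-up EQ-5D at month 12, and 11.3.1.4 and the visit schedule count from activation. These are editorial.

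**Conclusion.** The point holds as a low-severity gap in specification. The EQ-5D method does not deliver the within-man change that the synopsis and Table 6.1-1 describe, and no general rule supplies it. Its closest counterparts, IQoL and IIQ-7, do specify it, so this looks like a drafting omission.

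At 20% attrition, the subtraction a reader would make carries an artefact of one fifth of the completer-minus-dropout baseline gap: nil with no gap, and 2.0 to 4.0 VAS points for assumed gaps of 10 to 20. At an assumed correlation of 0.5, the standard error of the paired change is about 0.745 of the value from treating the columns as independent. The primary analysis, the sample size and the data collection are unaffected.

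**What to change.** - **Main change.** In Section 11.3.1.4.1, add the change-from-baseline clause already used for IQoL and IIQ-7. Report the within-man change to 12 months with a 95% confidence interval for EQ VAS, and for the index if it is derived, in men with both assessments.
- **Show the paired set.** Give the number of men with both forms and their baseline mean beside the baseline mean of all men with a baseline form. The gap between the two means displays the composition effect directly.
- **Optional.** Add a baseline-by-12-month shift table for each dimension of the descriptive system.
- **State the limit.** Say that the paired change describes men who returned both forms and does not correct for dropout related to poor outcome.
- **Editorial.** Align the EQ-5D timing in Table 6.1-1, and the reference point in the categorical sentence of 11.3.1.4.1, with Table 10.1-1, Section 10.9 and Section 11.3.1.4.

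The cost is a clause or two of text and a few extra table cells. No new data, visits or subjects are needed.

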11.3.1.5. Additional Endpoint 5 – Patient Ease of Use

To evaluate the patient use of device as measured by Patient Ease of Use Questionnaire at 6 months and 12 months post device activation.

The endpoint is the patient ease of use of the device.

11.3.1.5.1 Statistical Methods

The frequency and the proportion of a category will be calculated at 6 months and 12 months post device activation.

11.3.2. Interim Analyses

No formal interim analyses are planned for the purpose of stopping the study early for declaring effectiveness or for futility.

11.3.3. Subgroup Analyses

Treatment success rates will be calculated by three Pressure Regulating Balloon subgroups (Balloon FGS 51-60 cm, 61-70 cm, 71-80 cm), and Fisher's Exact test or Chi-squared test will be applied to evaluate if there is a correlation between treatment success and Pressure Regulating Balloons.

11.3.4. Justification of Pooling

Fisher's Exact test or Chi-squared test will be applied to evaluate the homogeneity of the treatment success rates across the study centers.

11.3.5. Multivariable Analyses

There are no planned multivariable analyses.

11.3.6. Changes to Planned Analyses

Any changes to the planned statistical analyses made prior to performing the analyses will be documented in an amended Statistical Analysis Plan approved prior to performing the analyses. Changes from the planned statistical methods after performing the analyses will be documented in the clinical study report along with a reason for the deviation.

12. Health Economics Outcomes

A formal health economics analysis may be conducted after the trial is completed, given meaningful clinical results are obtained. In addition to the primary clinical endpoints, the EQ-5D-5L questionnaire, a standardized instrument, will be collected prospectively in all subjects at baseline and 12-month follow up as a measure of non-disease-specific health-related quality of life and used to obtain health utility scores. The health economics analysis may take into consideration any differences in clinical endpoints, complication rates, quality of life, and resource utilization.

13. Data Management

13.1. Data Collection, Processing, and Review

Subject data will be recorded in a limited access secure electronic data capture (EDC) system.

The clinical database will reside on a production server hosted by Medidata EDC System. All changes made to the clinical data will be captured in an electronic audit trail and available for review by the sponsor or its representative. The associated Rave software and database have been designed to meet regulatory compliance for deployment as part of a validated system compliant with laws and regulations applicable to the conduct of clinical studies pertaining to the use of electronic records and signatures. Database backups are performed regularly.

The Investigator provides his/her electronic signature on the appropriate electronic case report forms (eCRFs) in compliance with local regulations. A written signature on printouts of the eCRFs must also be provided if required by local regulation. Changes to data previously submitted to the sponsor require a new electronic signature by the Investigator acknowledging and approving the changes.

Visual and/or electronic data review will be performed to identify possible data discrepancies. Manual and/or automatic queries will be created in the Medidata EDC system and will be issued to the site for appropriate response. Site staff will be responsible for resolving all queries in the database.

All access to the clinical database will be changed to "Read only" after all data is either "Hard Locked" or "Entry Locked". Once acceptance of the final report or finalization of publications (as applicable) is received, final database storage and archiving activities can begin. Once all of the closeout activities are completed a request to IT is submitted to have the "Database Locked" or Decommissioned and all database access revoked.

